In the last two decades, the evolution of neuroimaging modalities in the field of neurourology has provided a new frontier of research. In 1998, Blok et al. studied normal female micturition in 10 subjects with CNS PET imaging. Increased blood flow was demonstrated in the right dorsal pontine tegmentum and the right inferior frontal gyrus. (1) Other investigators have incorporated the use of fMRI to examine brain region activation during bladder filling (2), and voluntary pelvic floor muscle contractions (3, 4). Furthermore, others have published fMRI evidence of cortical neuroplastic changes after pelvic floor muscle training and biofeedback therapy for stress urinary incontinence (5). Krhut et al. used fMRI to preliminarily examine brain activity during bladder emptying, localizing areas in the parahippocampal gyrus, anterior cingulate gyrus, inferior temporal gyrus and inferior frontal gyrus during micturition (6). Our project to evaluate the normal healthy female subjects with concurrent urodynamics and fMRI has yielded valuable information regarding anatomical locations neuronal control in micturition. We completed the first part of current project (IRB [Pro00005508](#)) in July of 2013 and have reported our results at multiple scientific meetings. The manuscript is in progress currently. This would be second report in the literature on micturition with simultaneous UDS and fMRI and higher number of subjects. In summary all of our ten subjects were able to void while supine. Each patient was able to void at least three complete voiding cycles within the fMRI scanning phase, with time to initiate voiding and cystometric capacity as factors in total number of voiding cycles.

Group analysis of the patients (since all were able to void) yielded consistent areas of activation during the initiation of voiding (asterisks, Figure 1). These included regions for motor control (cerebellum, thalamus, caudate, lentiform nucleus, red nucleus, supplementary motor area, postcentral gyrus), emotion (anterior and posterior cingulate gyrus and insula), executive function (left superior frontal gyrus), as well as the parahippocampal gyrus, precuneus, cuneus, occipital lobe (visual stimulus), and a focal region in the midbrain.

[figure not shown]

Figure 1.

Brain Control of Voiding

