management for urinary symptom control in these patients. Despite having knowledge and data that Botulinum toxin A decreases the bladder contractility we have no human data how it affects the sensory efferent fibers to the brain and decreasing urgency and frequency. Our platform is a perfect model to study the effects of botulinum toxin A on sensory efferent fibers of the bladder and correlate that to the centers in the brain that respond to urgency and frequency. Thus we propose that patients who based on their clinical needs and exams are candidates for intravesical botulinum toxin A and have been a candidate in our study to have another fMRI with concurrent UDS about 8 weeks following their intravesical botulinum toxin A injection.

Purpose and Objectives

To perform functional MRI neuroimaging and data analysis on female subjects diagnosed with voiding dysfunction or neurogenic bladder during the act of micturition. Our goal with this pilot study is to determine whether BOLD signal changes on fMRI during voiding are substantial for data analysis. If so, data analysis will yield specific regions of the brain that are activated and/or deactivated during voiding. The second objective of this study is to determine whether concurrent urodynamics data gathered in the scanner can be correlated to fMRI data in order to elucidate simultaneous bladder function measurements with BOLD signal measurements.

Second objective of this study is to evaluate the sensory effects of intravesical injection of botulinum toxin A used for neurogenic detrusor activity.

Risk Category

(45 CFR 46.406) Category 3: Research involving greater than minimal risk and no prospect of direct benefit to the individual subject, but likely to yield generalizable knowledge about the subject's disorder or condition.

Research Design

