This is a pilot observational study in which brain activity will be observed via fMRI during simultaneous urodynamics testing. This study will examine the blood-oxygen-level-dependent (BOLD) signals during fMRI of the brain of subjects diagnosed with neurogenic bladder or dysfunctional voiding. BOLD signals are an indirect measure of neural activity that can be identified on fMRI. There are no known risks to a subject's fetus. There is no known teratogenic risk associated with urodynamics or fMRI. Patients will be screened with a urine pregnancy test at enrollment. Patients with a positive pregnancy test will be excluded from the study. As a pilot study, 50 subjects will be recruited to investigate the feasibility of the study. There is no control group because this study involving human subjects with both urodynamic and fMRI testing is complex, time-consuming, and expensive. In addition we can already use our data for the past two years on normal healthy females as our control. Furthermore, no investigator has published previously regarding simultaneous urodynamics and fMRI in patients with neurogenic bladder and dysfunctional voiding. Subjects diagnosed with neurogenic bladder (e.g. MS) and dysfunctional voiding would have already undergone baseline urodynamic studies as part of their routine care and will proceed to concurrent fMRI and urodynamics testing.

Brain Control of Voiding

Inclusion Criteria for subjects with voiding dysfunction and neurogenic bladder:

- Women ages 18 years or older
- Primary language is English
- Presence of lower urinary tract symptoms (urinary frequency, urgency, urge incontinence or difficulty emptying)
- Presence or history of neurologic illness or injury (spinal cord injury, spina bifida, Parkinson's, major spine surgery, multiple sclerosis, or other neurological disorders) and dysfunctional voiding.
- Performed baseline clinic urodynamics testing as part of routine urologic evaluation of voiding dysfunction within 24 months of scanning (if not done, will be performed as part of the study).

Exclusion Criteria for subjects with voiding dysfunction:

- Male
- Patients without lower urinary tract symptoms (urinary frequency, urgency, urge incontinence or difficulty emptying, etc)
- Positive urine pregnancy test at enrollment (There are no known risks to a subject's fetus. There is no known teratogenic risk associated with urodynamics or fMRI)
- Presence of active and symptomatic urinary tract infection

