This is a pilot study. These experiments are novel, as there is currently no similar study in the literature. There is no way to predict numbers required in order to find statistically variations between arms of each experiment. Pilot data from this study will aid in powering future studies on the same topic. This study involving human subjects with both urodynamic and fMRI testing is complex, time-consuming, and expensive. Furthermore, no investigator has published previously regarding simultaneous urodynamics

Brain Control of Voiding

and fMRI. This protocol is for a feasibility study. Once the feasibility of our model is established, we can work on studying control groups.

Data Analysis

Provide a description of your plan for data analysis. State the types of comparisons you plan (e.g. comparison of means, comparison of proportions, regressions, analysis of variance). Which is the PRIMARY comparison/analysis? How will the analyses proposed relate to the primary purposes of your study?

The data analysis will be similar to other data analytic strategies carried out in the laboratory. It requires fairly complex analysis techniques and is thus difficult to summarize without going into lengthy details. Briefly, our data analysis will be as follows: We have made extensive use of a general linear model in analyzing and designing our fMRI experiments. To compare data from different subjects, the scan data from each subject must be transformed into a standard anatomical framework. We follow the approach of Frackowiak et al (1997), which analyzes the brain into small local volumes or “voxels”. The fMRI signal from each voxel is then subjected to the following transformation steps:

Analysis Step 1: Spatio-temporal normalization to a standard brain map, and smoothing to improve the signal-to-noise ratio.

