Analysis Step 2: Statistical analysis to determine the significance of the activity measured at each voxel. We use an established statistical framework [K.J. Friston, et al., Human Brain Mapping 2, 189-210 (1995); K.J. Friston, A.P. Holmes, K.J. Worsley, Neuroimage 10, 1-5 (1999)] in terms of a general linear model, which incorporates and formalizes the independent explanatory variables in our experiment. Given the variance of each parameter, we can construct a t-statistic as a measure of the significance of differences in the parameters estimated from the different experiments, at different voxels, or in different subjects. In practice, we construct a statistic out of a particular linear combination of the parameters that describes a quantity of interest. To express this mathematically, we define a contrast vector that specifies a linear combination of parameters. Then the t-statistic is the quantity of interest divided by its standard error. When we calculate a t-statistic at each voxel in an imaged brain, measuring the significance of a difference between parameters from different subjects or different experimental conditions, the resulting set is called a statistical parametric map. We use such maps to determine areas of significant activation in the brain during presentation of stimuli or performance of the task.

A linear regression analysis will also be employed to look for covariance of behavioral variables with observed brain activity. For instance, the degree of preference for an image or the amount of prior exposure to the stimulus can be entered into the analysis as explanatory variables for the brain activation. In this case, the degree to which behavioral variables cause linear changes in brain activity can be illustrated by fitting the estimated response to the observed time series of dynamic blood flow in the brain. The regions identified in this type of analysis will be used to generate “regions of interest”, smaller areas of voxels that can be analyzed without making assumptions regarding the underlying hemodynamics. In this analysis, the raw change in magnetic signal can be read out and compared across any variable of interest.

Brain Control of Voiding

Potential Risks/Discomforts

Risks with Pregnancy:

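### The region-of-interest step permits regions selected by the regression to be compared again, in the same scans, on the urodynamic measure that selected them

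*Combined protocol and SAP*

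**What the plan says.** Under Purpose and Objectives, one aim is to "determine whether concurrent urodynamics data gathered in the scanner can be correlated to fMRI data".

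The Data Analysis section does not return to that aim by name. Analysis Step 2 describes a general linear model with voxelwise t-statistics and then adds: "A linear regression analysis will also be employed to look for covariance of behavioral variables with observed brain activity". The only covariates it mentions are examples: "the degree of preference for an image or the amount of prior exposure to the stimulus can be entered into the analysis as explanatory variables". Neither is collected according to the Study Procedure section or the appendices.

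The region-of-interest rule follows directly. "The regions identified in this type of analysis will be used to generate" regions of interest, and in these "the raw change in magnetic signal can be read out and compared across any variable of interest". The stated reason for using such regions is that they can be examined without a hemodynamic model.

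Under Sample Size, 50 subjects are planned with no power calculation, and the section says: "Pilot data from this study will aid in powering future studies on the same topic".

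**The concern.** If voxels are kept because their signal correlates with a variable, their average will correlate with that variable in the same data, even when nothing but noise was selected. A second test of that correlation is then not a test, and its size is not an estimate of the true association.

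The rule in Analysis Step 2 leaves this open. The regression selects the regions, the same scans supply the read-out, and the comparison variable is unrestricted. Put a urodynamic measure into the regression and the objective could be reported through a correlation that the selection itself has inflated. Because the pilot is meant to inform the size of later studies, such a figure could also be carried forward as a planning effect.

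**Working it through.** **1. What the text allows.** The wording covers three uses of a regression-selected region.

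| Use of the region in the same scans | Consequence |
|---|---|
| Plot the raw time course | Harmless |
| Compare on a variable unrelated to the selecting one | Harmless |
| Compare on the selecting variable, or one correlated with it | Effect inflated, p-value invalid |

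Up to 5 urodynamic and scanning cycles are recorded per session (fMRI Scanning Visit), but no cycles or subjects are held out to define regions. No anatomical definition is given.

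**2. Inputs.** From the documents: n = 50. The plan states no threshold, voxel size, smoothing, or level at which urodynamics enter the model, so there is no figure of its own to reproduce. Assumed: one urodynamic value per subject, true correlation 0, selection at two-sided p<0.001 per voxel, read-out tested at two-sided 0.05.

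**3. Single-voxel check.** With n − 2 = 48 degrees of freedom, the selection cutoff is t = 3.505, so

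c = t/√(n − 2 + t²) = 3.505/√(48 + 12.29) = 0.451.

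The cutoff for p<0.05 is t = 2.011, which gives r = 0.279. Every selected voxel exceeds 0.451 and therefore passes 0.279.

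Under a true correlation of zero, the density of r is proportional to (1 − r²)^((n−4)/2). The mean absolute correlation of an unselected voxel is then m = 0.115. Given selection at level p, the mean is

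m × (1 − c²)^((n−2)/2) / p = 0.115 × (0.796)^24 / 0.001 = 0.115 × 0.00421 / 0.001 ≈ 0.48.

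Selection alone moves the expected absolute correlation from 0.115 to 0.48. Averaging voxels into a region raises it further, because the voxel noise averages out while the shared selected component stays.

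**4. Region-level simulation, n = 50, true correlation zero.** Two designs were run:
- A: smoothed maps of 47,912 voxels (3 mm, 8 mm smoothing), largest cluster taken as the region, 250 runs.
- B: 5,000 independent voxels, all positively selected voxels averaged, 300 runs, of which 28 gave no region.

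| Read-out | Design A | Design B |
|---|---|---|
| Same data, selecting variable: mean correlation (absolute in A) | 0.58 to 0.62 | 0.65 |
| Same data, selecting variable: p<0.05 | 100% | 100% |
| Same data, variable correlated 0.5 with it: p<0.05 | 59% to 62% | 65% |
| Same data, unrelated variable: p<0.05 | 5% to 6% | 3% |
| Region fixed in advance (A) or independent data (B): p<0.05 | 6% (mean absolute correlation 0.11) | 4% |

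The Design A ranges cover minimum cluster sizes of 1, 5 and 10 voxels. At 20 or more voxels the mean was 0.66, but only about 10 runs (4% of 250) produced such a cluster. With a whole-brain corrected threshold it was 0.65, from about 15 runs (6% of 250). Those two figures are imprecise, but they suggest that a stricter threshold does not remove the inflation once a region has been found.

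**5. What was not simulated.** A time-linked analysis within subjects, over repeated cycles, was not run. The direction of the bias is the same there, but the figures above do not carry over.

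**The case against.** The strongest reply is that the text permits circular use without prescribing it. It specifies no test of the selecting variable, and its stated purpose for the regions fits a descriptive time-course plot. That stands. A reader might infer that the plan commits itself to a circular test; the documents do not say so.

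A reader might also infer that the read-out creates a false positive answer to the objective. It does not. By the time a region exists, the whole-brain regression has already given its answer. In Design A, at least one null region appeared in 100%, 94%, 41% or 4% of runs for minimum clusters of 1, 5, 10 or 20 voxels, and in 6% with a corrected threshold. Those rates are set by an assumed threshold, and the plan states none. This is a multiplicity question, separate from the read-out. Likewise, the 100% nominal significance follows by construction.

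A third tempting step is to turn a correlation of 0.6 into a sample size for the next study and declare it too small. The documents give no true correlation to measure that against. They also do not say that a region-of-interest correlation would be the planning effect.

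Finally, the aim of relating simultaneous bladder and BOLD measurements may well mean a within-subject, time-linked analysis. This limits the figures to illustration. The missing urodynamic variable is, on its own, a detail that the analysts could supply. None of these replies supplies the missing safeguard: nothing in the section confines the read-out to harmless uses.

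**Conclusion.** The concern holds as a permitted misuse. As written, Analysis Step 2 allows a region picked for its correlation with a urodynamic measure to be compared on that measure, or a related one, in the same scans. Such a comparison overstates the association and has no valid p-value. It does not itself add false-positive regions.

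Under the stated assumptions (50 subjects, one value each, true correlation zero, p<0.001 per voxel), the overstatement is from about 0.11 to about 0.6 in absolute correlation. That is a guide to scale and not a forecast for this trial. The pilot label does not remove the problem, because the pilot's results are intended to inform the power of later studies. The text should be changed before analysis.

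**What to change.** Amend Analysis Step 2 along these lines:

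- For any inferential comparison on a urodynamic measure, define the regions independently of the regression on that measure. Use anatomical regions for the areas listed in the background text on the first part of the project, or leave-one-subject-out selection.
- The voiding map from the ten healthy women (the "consistent areas of activation during the initiation of voiding") may define regions for correlations within patients. It should not define them for the patient-versus-healthy comparison. Research Design names those women as the control ("we can already use our data for the past two years on normal healthy females as our control"), and regions chosen for their activation would favour their group.
- Label any read-out from regression-selected regions in the same data as descriptive, with no p-value and no effect size used in future power calculations.
- In the same edit, replace the image-preference and stimulus-exposure examples with the urodynamic variables recorded in the scanner.

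The cost is protocol wording and modest analysis work. No new scans are needed. The drawback is that regions fixed in advance can miss an area specific to patients; the whole-brain regression stays in the plan and still covers that.

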The second visit will be the fMRI scanning session at the Methodist Hospital. Subjects will be instructed to arrive 30 minutes prior to scanning. Subjects will have a dip stick urinalysis performed and a urine pregnancy test to confirm that they are not pregnant prior to the insertion of the catheters and the MRI. Urodynamics catheters will be inserted. After task instruction, subjects will be placed in the scanner. Task instruction consists of giving subjects directions to hold their urine, relax their pelvic muscles, and void will be conveyed to them via instructions printed on a screen they will see while in the scanner. Patients will also be instructed to squeeze a bulb in their hand if they experience claustrophobia or discomfort, and want to be removed from the scanner. Scanning will then begin.

After standard localizer and structural scans, the functional sequence and urodynamics will start. The bladder will be filled with sterile saline, as per urodynamics procedure. Subjects will be instructed (visually using a projection screen and mirror, standard procedure for the HNL) to hold their bladder, and then view a fixation cross for 30 seconds. They will be asked to indicate, via finger button, when their bladder is full. Subjects will then be instructed (again using a projection screen and mirror) to relax their pelvic floor muscles, and then to urinate. The experiment will conclude with the subject pressing the finger button to indicate they are finished urinating. At that point an instruction to relax will appear and then be replaced by a fixation cross that the subject will view it for 30 seconds and the experiment will be complete. The urodynamic and scanning cycle may be repeated up to 5 cycles.

4) repeat fMRI scanning visit:

This visit would only apply to the patients that clinically were a candidate for intravesical injection of botulinum toxin A and went on receiving it as a part of their routine care. If they agree, we would recruit them for a repeat fMRI scan just as detailed above about 8 weeks (+/- 4 weeks) following their botox injection. Urogenital Distress Inventory (UDI-6), Incontinence Impact Questionnaire (IIQ-7), and the Hamilton Anxiety Rating Scale (HAM-A) will be re-obtained at this visit.

Sample Size

How many subjects (or specimens, or charts) will be used in this study?

Local: 50 Worldwide: 50

Please indicate why you chose the sample size proposed:

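### The region-of-interest step names raw signal change as its measure and no intensity scaling, so region comparisons between women or sessions have no stated common unit

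*Combined protocol and SAP*

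**What the plan says.** The main analysis (Data Analysis, Analysis Step 2) is a voxelwise general linear model giving maps of t-statistics: "Then the t-statistic is the quantity of interest divided by its standard error". A linear regression on behavioral variables then picks out regions of interest, described as "smaller areas of voxels that can be analyzed without making assumptions regarding the underlying hemodynamics". The measure for those regions is given in one sentence: "In this analysis, the raw change in magnetic signal can be read out and compared across any variable of interest".

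The preprocessing is in Analysis Step 1: "Spatio-temporal normalization to a standard brain map, and smoothing to improve the signal-to-noise ratio". Its stated purpose is anatomical, since "the scan data from each subject must be transformed into a standard anatomical framework". Neither step names division by a baseline, percent signal change, grand-mean or global scaling, or a session or scanner term.

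Two comparisons across sets of scans appear elsewhere. Research Design says of the earlier healthy women: "In addition we can already use our data for the past two years on normal healthy females as our control". Study Procedure, item 4, covers women who receive botulinum toxin in routine care: "we would recruit them for a repeat fMRI scan just as detailed above about 8 weeks (+/- 4 weeks) following their botox injection".

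**The concern.** MR signal intensity has no absolute unit. Its level depends on receiver gain, coil position and image scaling, which can differ between women and between two sessions of one woman. For a fixed percent BOLD response, the raw change is proportional to that level. Alignment to a standard brain map makes locations comparable, not intensities.

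The open-ended list of comparison variables excludes neither group nor session. A questionnaire score collected once per visit can be compared only between women or between visits. In any such region comparison, unscaled values carry the scaling differences with them. Random differences add noise. A difference that runs systematically between two sets of scans is added to the estimated contrast.

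The study is also a pilot whose data are meant to help power later studies (Sample Size). Effect sizes and SDs in arbitrary units would carry over poorly.

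**Working it through.** The plan gives no signal intensities, effect sizes, SDs, alpha or power, so there is no figure to reproduce. What follows is illustration.

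**Inputs from the documents.** 50 subjects (Sample Size); ten earlier healthy women (background: "In summary all of our ten subjects were able to void while supine"); one repeat scan after injection (Study Procedure, item 4). The number of women who will be rescanned is not given, so 10, 20 and 50 are used as a range, 50 being the ceiling.

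**Inputs assumed.** Mean percent signal change 1.0, SD 0.5, correlation 0.5 between a woman's two sessions, two-sided 0.05, random gain SD 0 to 0.3 on the log scale, systematic gain ratio 1.0 to 1.2.

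**Step 1: the unit.** Let g be gain, S the baseline and p the percent response. Then raw change = g × S × p/100, and percent signal change = 100 × (g × S × p/100)/(g × S) = p.

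With S = 1000 and p = 1, raw change is 8.0 at g = 0.8 and 12.5 at g = 1.25; percent change is 1 at both. Equally, two women with assumed baselines of 600 and 900 and the same 1% response give 6 and 9 units, a ratio of 1.5. That describes two hypothetical women and does not estimate bias in a group mean.

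**Step 2: gain varying only at random.** With no true difference (20,000 simulated trials per setting, gain SD 0 to 0.2), raw units reject in 4.9% to 5.3% of trials, so there is no inflation. The cost is power. For a true fall from 1.0% to 0.7% in 20 women, paired test:

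| Random gain SD | Power, raw | Power, percent |
|---|---|---|
| 0.1 | 69% | 73% |
| 0.2 | 61% | 73% |
| 0.3 | 50% | 72% |

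**Step 3: gain shifted systematically.** False-positive rates in raw units, with no true difference; ranges cover random gain SD 0 to 0.2:

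| Comparison | 10% shift | 20% shift |
|---|---|---|
| 50 patients vs 10 healthy (Welch) | 7-8% | 11-15% |
| Before/after, n = 10 | 7-8% | 13-17% |
| Before/after, n = 20 | 10-13% | 25-33% |
| Before/after, n = 50 | 20-26% | 56-71% |

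A hand check for n = 20, 10% shift and no random gain: the bias is (1.1 − 1) × 1.0 = 0.10. The SD of the difference is √(0.25 + 1.21 × 0.25 − 2 × 1.1 × 0.5 × 0.25) = 0.527, so the standard error is 0.527/√20 = 0.118. The bias is 0.10/0.118 = 0.85 standard errors, in line with the simulated 12.5%. It does not shrink as women are added, which is why the rate rises with n.

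**Step 4: percent signal change.** Rejection is 4.7% to 5.4% in every Step 3 scenario and those without a shift, because the gain cancels.

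**The case against.** A reader might infer that the plan commits to comparing unscaled signal before and after toxin, and between patients and healthy women, so that those results will be biased. The documents do not support that, for four reasons, all of which stand.

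- The wording is permissive, for a follow-on step. The main inference is the voxelwise map, and the first objective (whether BOLD changes during voiding are substantial, and where) rests on contrasts within a woman's own scan, which a difference in gain between sessions does not bias.
- Coming straight after the remark about hemodynamic assumptions, raw may mean not model-fitted rather than unscaled. The plan also calls its analysis text a brief account of complex laboratory practice and does not define the temporal part of its normalization.
- No passage ties the region read-out to the toxin or healthy-control comparison. Sample Size even defers work on control groups, although Research Design says the healthy data can already serve.
- Nothing shows a systematic intensity shift. One 3 T scanner is mentioned, and the repeat scan is to follow the same procedure. Whether scanner and settings match those of the earlier healthy scans is not said.

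These points limit the claim without removing it. Raw signal change is still the only region measure named, and a literal reading gives values without a common unit.

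A further objection is that the denominator is itself a choice, because the two 30-second fixation periods fall in different bladder states. It does not defeat the remedy. Reference levels within one run and region should differ only by about the size of the BOLD change, about 1% under the assumption above, so dividing 10 units by 1000 or by 1010 gives 1.00% or 0.99%. Any of these references removes the scaling. The choice still defines what the change is measured from, so one must be named and used throughout.

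**Conclusion.** The point holds as a cheap improvement. The plan names a region measure with no common unit across women or sessions, and a better one is available from the same data.

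The established consequence is conditional: if unscaled values are compared between women or sessions, random scaling loses power (from about 73% to 61% at an assumed gain SD of 0.2 with 20 women) and does not raise the false-positive rate. The larger harm, scaling read as a group or toxin difference, needs two further conditions: that the read-out is used for that comparison, and that intensity differs systematically between the two sets of scans. The documents neither establish nor exclude either. The rates of 7% to 26% for a 10% shift and 11% to 71% for a 20% shift show sensitivity under assumed values; they do not predict what will happen in this study. Within-run contrasts and the voxelwise maps are outside this point.

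**What to change.** In Data Analysis, Analysis Step 2, replace the raw-signal wording with: percent signal change relative to one named reference (for example the first fixation period, or the run mean) in the same woman, run and region. Use that reference for every region comparison between women or between sessions. Report mean region intensity per session as a check. State whether scanner and settings match across sessions and with the earlier healthy scans.

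The cost is a few sentences, one extra division per region, and fixing the reference period in advance. No new data are needed.
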